6.2.7. Periods Start and End Dates

Adverse events will also be summarized by periods below:

- Part I Titration Period
 - Start Date - the Day 1 visit;
 - End Date - the last dose of study treatment during titration period (up to and including Week 8 visit).
- Part I Maintenance Period

For patients who completed any assessments after Week 8 visit, the start and end dates are:

 - Start Date - the day after Week 8 visit;
 - End Date - the Part I last dose date .
- Part II and III Treatment Period

For patients who are randomized

 - Start Date - the start date of Part II;
 - End Date - the last dose of study treatment during the study.
- Follow-up Period
 - Start Date - the day after the last dose of study treatment;
 - End Date - the day of the last visit.

Periods are not corresponding to Parts. Events occurred after last dose of study treatment are included with each Parts, but are not included period. Events after the last dose of study treatment will all be summarized with the follow-up period.

This document is confidential.

Statistical Analysis Plan for Interventional Studies

Sponsor: Teva Branded Pharmaceutical Products R&D, Inc./Nuvelution TS Pharma, INC.
 Protocol No.: TV50717-CNS-30047

6.2.8. Exposure-Adjusted Incidence Rate

Exposure-Adjusted Incidence Rate (EAIR) is calculated as the number of patients with an AE divided by patient-years of treatment. For calculating patient years, patients with an AE contribute with treatment exposure up to the day of their first contributing AE, patients without an AE contribute their entire treatment duration in the Part or Periods event.

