- Parts I and III combined, based on the Safety Analysis Set. The events that occurred in Part II will not be included. Table will contain one overall column. All tables will include number, frequency of patients with the event, and EAIR. All AE tables will be prepared for Part I and III combined.

This document is confidential.

Statistical Analysis Plan for Interventional Studies

Sponsor: Teva Branded Pharmaceutical Products R&D, Inc./Nuvelution TS Pharma, INC.
Protocol No.: TV50717-CNS-30047

- Part II is based on the RWSAF population and presented by the actual treatment received during the randomized withdrawal period. Table will include number and frequency of patients with the event. All AE tables will be prepared for Part II.
- Parts I, II, and III combined, based on the Safety Analysis Set. Table will contain one overall column. The Parts I, II, and III combined tables will be presented for entire study and by each Part. All tables will include number, frequency, and the EAIR. The overview of AEs, AEs by SOC and preferred terms, and the SMQ summaries will be presented for Parts I, II, and III combined.
- Periods, based on the Safety Analysis Set. Table will contain one overall column. All tables will include number, frequency, and the EAIR. The overview of AEs and AEs by SOC and preferred terms will be presented by periods.

For summary of patient, the following rules will apply:

1. Patients having more than 1 event with the same PT will be counted once for that term.
2. Patients having more than 1 event with the same SOC will be counted once for each event and once for that SOC.
3. For tabulations by severity, only a patient's most severe event within the category (e.g. overall, SOC, PT) will be counted; similarly, for tabulations by relationship, only a patient's most related event within a category will be counted. The denominator for percentages will be the number of patients in Safety Analysis Set for the given treatment group or overall (i.e., the N's for the columns).

For the summary of incidence rate, all events will be included.

Listings will be provided for all AEs and the following subsets:

- All TEAEs
- Serious TEAEs
- TEAEs leading to study drug discontinuation
- TEAEs leading to dose interruption
- TEAEs leading to dose reduction
- TEAEs leading to death.

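### The adverse-event rate rules in SAP 6.2.6 to 6.2.8 and 9.4 do not match numerators to person-time, and the Follow-up Period rate has a zero denominator

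*SAP*

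**What the plan says.** SAP 6.2.8 defines the rate: "Exposure-Adjusted Incidence Rate (EAIR) is calculated as the number of patients with an AE divided by patient-years of treatment". It gives two person-time rules: "patients with an AE contribute with treatment exposure up to the day of their first contributing AE", and "patients without an AE contribute their entire treatment duration in the Part or Periods event".

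SAP 6.2.7 defines the Follow-up Period by "Start Date - the day after the last dose of study treatment" and adds: "Events after the last dose of study treatment will all be summarized with the follow-up period". The same section says that events after the last dose do belong to the Parts, though not to the treatment Periods.

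SAP 6.2.6 ends Part III at the Week 56 visit for completers and at the last dose for patients who stop earlier. SAP 3.7 plans up to 54 weeks of dosing.

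SAP 9.4 bases the Period tables on the Safety Analysis Set with one overall column and requires: "All tables will include number, frequency, and the EAIR". It makes no exception for Follow-up. The combined tables for Parts I, II and III use the same set and are also shown by Part. After its rules for counting patients, 9.4 says: "For the summary of incidence rate, all events will be included". On percentages it says: "The denominator for percentages will be the number of patients in Safety Analysis Set for the given treatment group or overall", and identifies that number with the column N. The stand-alone Part II tables use the randomized withdrawal safety population by actual treatment and show no exposure-adjusted rate.

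**The concern.** Long-term safety is the primary objective (SAP 3.1), and adverse-event incidence is the first safety endpoint listed (SAP 4.1). A rate can be interpreted only if the events in the numerator arise during the time in the denominator, and if one rule says whether patients or events are counted. The sections above leave four gaps:

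1. A required rate with no person-time (Follow-up).
2. Part III events counted over a longer window than its person-time, with completers and discontinuers treated differently.
3. Two conflicting statements about what enters the numerator.
4. Percentages for later intervals that, read literally, include patients who never reached them.

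Two programmers working from this text could produce different tables and both claim to follow the SAP.

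**Working it through.** The SAP states no adverse-event rate or percentage, so there is no figure to reproduce. The definitions are applied directly. Event rates and numbers entering later phases are assumptions, because the SAP gives none.

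**1. Follow-up Period.** For a completer on the nominal schedule the last dose is Day 378, and the Period runs from Day 379 to Day 392. Treatment days inside it = max(0, 378 − 379 + 1) = 0. This holds for every patient by definition, so the rate is n/0. Follow-up time would instead give about 14 days per completer.

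**2. Part III.** Treatment covers Weeks 31 to 54, which is 24 weeks. The completer's event window covers Weeks 31 to 56, which is 26 weeks. Assume a constant rate L per year, equal on and off drug.
- Ratio of the SAP rate to L = (1 − exp(−L × 26 weeks)) / (1 − exp(−L × 24 weeks)).
- L = 0.25, 0.5, 1, 2 gives 1.078, 1.073, 1.064, 1.049.
- The upper limit, for rare events, is 26/24 = 1.083, an excess of 2/24 = 8.3%.
- For Parts I and III combined, treatment is 28 + 24 = 52 weeks, so the limit is 2/52 = 3.8%.

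Separately, 6.2.6 closes Part III at the last dose for a discontinuer, so a post-dose event in that patient falls outside it. SAP 6.2.7 says post-dose events are included in the Parts. Both cannot apply.

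**3. Numerator.** SAP 6.2.8 counts patients, once each, over time cut at the first event. SAP 9.4 admits all events to the incidence rate, and 6.2.8 defines the only such rate in the SAP. To see how far apart the rules are, suppose both were applied at once, so that all events are divided by first-event time, over 52 weeks (T = 0.997 year):
- Events per patient = L × T. First-event time per patient = (1 − exp(−L × T)) / L.
- Ratio of the hybrid rate to L = L × T / (1 − exp(−L × T)).
- L = 0.25, 0.5, 1, 2 gives 1.13, 1.27, 1.58, 2.31.
- At rates nearer to a single preferred term, L = 0.05 and 0.1, the excess is about 2.5% and 5%.

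**4. Percentages.** If a fraction f of the Safety Analysis Set enters an interval, the displayed percentage is f times the percentage among entrants. As an illustration, take 20 affected patients in the Part II and III Treatment Period, and 157 patients in the Safety Analysis Set (the number enrolled at 09 Aug 2019 in SAP Table 2, assuming all were dosed). The displayed figure is 20/157 = 12.7%. Among entrants it would be:
- 80 entered: 25.0%
- 100 entered: 20.0%
- 120 entered: 16.7%
- 140 entered: 14.3%

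**The case against.** Much can be said in the plan's defence.

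- **Follow-up rate.** SAP 13.2.5.2 has statistics that cannot be estimated reported as NE. The gap would be visible, counts and percentages would still appear, and Period displays are limited to the overview and the table by system organ class and preferred term. This stands as to harm, but the SAP still requires an output that cannot exist.
- **All events.** The sentence follows the once-per-patient and most-severe rules. It may mean only that those rules drop no event from consideration for the rate. That reading is possible but not written. A reader might infer that reported rates will be inflated by 27%, 58% or 131%. The documents do not support this: no section prescribes all events over first-event time. The hybrid arises only by joining two conflicting sentences, at assumed rates.
- **Part III.** The mismatch is small, affects only patients who reach Week 56, and raises the reported rate, so it does not flatter the drug. This stands.
- **Percentages.** The denominator sentence sits inside the rule on severity and relationship and points to column Ns. SAP 6.2.7 defines the later Periods only for patients who reached them. SAP 13.2.5.2 says the denominator is usually the patients exposed, with details in footnotes. This leaves room for the right denominator but does not fix it, because the Period tables and by-Part display are expressly based on the Safety Analysis Set. A reader might infer that all Part percentages are diluted. They are not: the stand-alone Part II tables use their own population.
- **Late-phase safety.** A reader might also infer that Part III will look safer merely because patients left. The exposure-adjusted rate in the same tables is free of that dilution, since patients who never entered add no time, and disposition and exposure by Part are reported too.

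**Conclusion.** The point holds as a set of definitions to reconcile. The Follow-up rate is undefined for every patient, and this needs no assumption. The Part III rate is overstated by at most about 8% (4% for Parts I and III combined) if event rates are equal on and off drug, and the handling of post-dose events in discontinuers is contradictory. The all-events sentence conflicts with the definition in 6.2.8. Its effect cannot be sized from the SAP, and the ratios above show only how far apart the two rules can lie. Dilution of percentages applies, on the literal reading, to Period tables and by-Part columns, and its size depends on unstated dropout.

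Severity is moderate. These displays serve the primary objective, but they are descriptive, no treatment comparison in Part II uses the exposure-adjusted rate, and all events are listed.

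**What to change.** 1. Omit the exposure-adjusted rate for the Follow-up Period, or compute it over follow-up person-time and label it so.
2. Make the event window and person-time coincide for each Part: either limit the events in the rate to treatment time, or add the off-drug time to the denominator. Apply one rule to completers and discontinuers, and align 6.2.6 with 6.2.7.
3. State in 6.2.8 that the numerator is patients with a first event in the Part or Period. Delete the all-events sentence in 9.4, or turn it into a separately labelled rate of events per total person-time without censoring at the first event.
4. For Period tables and by-Part columns, set the percentage denominator to the Safety Analysis Set patients who entered that Part or Period, and show that N. Leave the stand-alone Part II tables as they are.

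The cost is SAP wording and programming, with no new data. Some late-phase percentages will become less favourable.

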6.3. Missing Data

In general, only the observed data from the patients will be used in the statistical analyses. No data imputation will be applied for missing values.

6.4. Visit Windows

For efficacy and safety by-visit analyses, data collected at post baseline scheduled visits will be included using their scheduled visit and data collected at early termination and unscheduled visits will be included and assigned to a visit window as described below.

Efficacy: Visit Windows for Unscheduled or Early Termination Visit

Assessment	Study Day Window	Scheduled day	Scheduled Visit/Week
YGTSS	Day 2 - 21	Day 14	Week 2
	Day 22 - 42	Day 28	Week 4
	Day 43 - 80	Day 56	Week 8
	Day 81 - 150	Day 105	Week 15
	Day 151 – Date of first dose of double-blind IMP (or Date of randomization, if first dose date is missing) if patient is randomized; Day 151 – Day 203 if patient is not randomized	Day 196	Week 28/Beginning of Part II
	Day after Part II first dose (or Date of randomization, if first dose date is missing) - Week 30 visit date (or Day 224 if subject terminated before Week 30 visit)	Day 210	Week 30
	Day after Week 30 visit - 262	Day 238	Week 34/Part III
	Day 263 - 332	Day 287	Week 41
	Day 333 - 382	Day 378	Week 54
	≥Day 383	Day 385	Week 55
TS-CGI, TS-PGI, Tic-free Interval	Day 2 - 42	Day 28	Week 4
	Day 43 - 80	Day 56	Week 8
	Day 81 - 150	Day 105	Week 15
	Day 151- 217	Day 196	Week 28/Beginning of Part II
	Day 218 - 262	Day 238	Week 34/Part III
	Day 263 - 332	Day 287	Week 41
	Day 333 - 382	Day 378	Week 54

This document is confidential.

Statistical Analysis Plan for Interventional Studies

Sponsor: Teva Branded Pharmaceutical Products R&D, Inc./Nuvelution TS Pharma, INC.

Protocol No.: TV50717-CNS-30047

Assessment	Study Day Window	Scheduled day	Scheduled Visit/Week
	≥Day 383	Day 385	Week 55
CY-BOCS	Day 2 - 118	Day 42	Week 6
	Day 119- 217	Day 196	Week 28/Beginning of Part II
	Day 218 - 308	Day 238	Week 34/Part III
	Day 309 - 382	Day 378	Week 54
	≥Day 383	Day 385	Week 55
C&A-GTS-QOL	Day 2 - 118	Day 42	Week 6
	Day 119 - 217	Day 196	Week 28/Beginning of Part II
	Day 218 - 308	Day 238	Week 34/Part III
	≥ Day 309	Day 378	Week 54

Safety: Visit Windows for Unscheduled or Early Termination Visit

Assessment	Study Day Window	Scheduled day	Scheduled Visit/Week
CDI-2, C SSRS	Day 2 - 21	Day 14	Week 2
	Day 22 - 42	Day 28	Week 4
	Day 43 - 80	Day 56	Week 8
	Day 81 - 150	Day 105	Week 15
	Day 151 – Date of first dose of double-blind IMP (or Date of randomization, if first dose date is missing) if patient is randomized; Day 151 – Day 203 if patient is not randomized	Day 196	Week 28/Beginning of Part II
	Day after Part II first dose (or Date of randomization, if first dose date is missing) - Week 30 visit date (or Day 224 if subject terminated before Week 30 visit)	Day 210	Week 30
	Day 225 - 262	Day 238	Week 34/Part III
	Day 263 - 332	Day 287	Week 41
	Day 333 - 382	Day 378	Week 54
	≥Day 383	Day 385	Week 55
Vital sign, Weight, Height	Day 2 - 21	Day 14	Week 2
	Day 22 - 35	Day 28	Week 4
	Day 36 - 49	Day 42	Week 6
	Day 50 - 80	Day 56	Week 8
	Day 81 - 150	Day 105	Week 15
	Day 151 – Date of first dose of double-blind IMP (or Date of randomization, if first dose date is missing) if patient is randomized; Day 151 – Day 203 if	Day 196	Week 28/Beginning of Part II

This document is confidential.

Statistical Analysis Plan for Interventional Studies

Sponsor: Teva Branded Pharmaceutical Products R&D, Inc./Nuvelution TS Pharma, INC.
 Protocol No.: TV50717-CNS-30047

Assessment	Study Day Window	Scheduled day	Scheduled Visit/Week
	patient is not randomized		
	Day after Part II first dose (or Date of randomization, if first dose date is missing) - Week 30 visit date (or Day 217 if subject terminated before Week 30 visit)	Day 210	Week 30
	Day 218 - Day 231	Day 224	Week 32
	Day 232 - 262	Day 238	Week 34/Part III
	Day 263 - 332	Day 287	Week 41
	Day 333 - 382	Day 378	Week 54
	≥Day 383	Day 385	Week 55
ECG	Day 2 - 42	Day 28	Week 4
	Day 43 - 126	Day 56	Week 8
	Day 127 - 287	Day 196	Week 28
	≥ Day 288	Day 378	Week 54
Chemistry/ Hematology/ Urinalysis	Day 2 - 126	Day 56	Week 8
	Day 127 - 287	Day 196	Week 28
	≥ Day 288	Day 378	Week 54

After mapping the data to the analysis visits of unscheduled and early termination visits, the following rules will apply unless other handling is specified for a particular analysis.

- If there is a scheduled visit in the analysis window, the scheduled visit will be selected.
- If there is no scheduled visit, but an early termination visit, the early termination visit will be selected.
- If there are no scheduled or early termination visits, the record closest to the planned assessment day will be selected for analysis.
- If there are no scheduled or early termination visits, and 2 records are equidistant from the scheduled day, then the later record will be selected.
- If a patient has no scheduled record or early termination/unscheduled visits in an analysis window, the patient will be considered missing at that visit.

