Visit window (days)	±3 from week 21			±3	±3 days						±3 from week 54		
In-clinic visit	X		X		X		X	X		X	X		X
Telephone contact		X		X		X			X			X	
Evaluate/Adjust IMP			X	X	X	X							X
Informed consent/assent													
Vital signs and weight ^e	X ^f		X		X		X	X		X ^b	X		X
Physical examination	X		X							X			X ^c
Neurological examination										X			X ^g
Height	X		X		X		X	X		X	X		X ^g
12-lead ECG ^h	X									X			X ^g
Chemistry/Hematology/Urinalysis	X									X			X ^g
Urine drug screen													X ^g
β-HCG test ⁱ	X						X			X			X ^g
CDI-2 (Parent and Self-Report) ^j	X		X				X	X		X	X		X ^g
Children's C-SSRS (Baseline/Screening) ^k													
Children's C-SSRS (Since Last Visit) ^k	X		X				X	X		X	X		X ^g
YGTSS ^{l, m}	X		X				X	X		X	X ⁿ		
TS-CGI ^m	X						X	X		X	X		

This document is confidential.

Statistical Analysis Plan for Interventional Studies

Sponsor: Teva Branded Pharmaceutical Products R&D, Inc./Nuvelution TS Pharma, INC.

Protocol No.: TV50717-CNS-30047

	Part II			Part III									U
	Randomized drug withdrawal			Maintenance (resumed) or titration post-drug withdrawal			Maintenance			Follow-up			
Study week ^a	28 ^b (Day 196)	29 (Day 203)	30 (Day 210)	31 (Day 217)	32 (Day 224)	33 (Day 231)	34 (Day 238)	41 (Day 287)	47 (Day 329)	54/ET ^c (Day 378)	55 (Day 385)	56 ^d (Day 392)	
Visit window (days)	±3 from week 21			±3	±3 days						±3 from week 54		
TS-PGII ^m	X						X	X		X	X		
TS-PGIS ^m	X						X	X		X	X		
Tic-free Interval ^k	X						X	X		X	X		
CY-BOCS ^k	X						X			X	X ^o		
C&A-GTS-QOL (including VAS) ^k	X						X			X			
Contact IRT and dispense IMP and patient diary	X ^p		X ^p		X ^p		X ^q	X ^q					X ^{g, r}
Collect IMP	X		X		X		X	X		X			X ^g
Assess IMP accountability/compliance/supply	X	X ^s	X	X ^s	X	X ^s	X	X	X ^s	X			X ^g
Assess adverse events	X	X	X	X	X	X	X	X	X	X	X	X	X
Concomitant medications ^t	X	X	X	X	X	X	X	X	X	X	X	X	X

^a Assessments to occur at end of study week (±3 days).

^b At the week 28 visit, the patients will be randomized 2:1 to their current dose of TEV-50717 or placebo in order to check for return of symptoms.

^c For patients who withdraw prematurely, an early termination visit should be conducted as soon as possible after the last dose of IMP. All patients who discontinue early will have a follow-up telephone contact for safety evaluation 2 weeks after their last dose of IMP; evaluations will be as described for week 54 visit.

^d This visit is a telephone contact for safety evaluation.

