6.1. General Methods

Statistical methodology and analyses are in accordance with the principles outlined by the ICH E9 guidelines. All statistical analyses will be conducted using SAS statistical software version 9.4 or above.

Tables, listings and figures (TLFs) will be produced in accordance with the principles outlined by the ICH E3 guidelines.

Data summaries will use descriptive statistics (number of patients [n], mean, standard deviation [SD], standard error [SE], median, minimum, and maximum) for continuous variables, and frequency and percentage of patients for categorical and ordinal variables, unless otherwise specified. For continuous variables, if $n < 5$ then only median, min and max will be presented.

Unless otherwise specified, all statistical tests will be two-tailed using a 0.05 level of significance. All confidence intervals (CIs) will be two sided 95% CIs.

Only visits mapped to scheduled visits will be included in by-visit summaries. All visit assessment data will be included in shift tables and will appear in the patient listings.

In general, endpoints assessed in Parts I and III will be summarized for Parts I and III combined and endpoints assessed in Part II will be summarized separately for Part II.

For assessments conducted at each visit, analyses for Parts I and III combined will include Week 28 assessment, but Week 30 assessment will not be included. Summary for Part II will include Week 28 (the randomized withdrawal baseline) and Week 30.

For analyses performed by time period, the date of Week 28 and Week 30 will be considered as the first and last day of Part II, respectively. Summary for Parts I and III combined will not include period between Week 28 assessment and Week 30 assessment, which will be covered under Part II summary.

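### For patients who attended Week 30, the CDI-2/C-SSRS and vital-signs visit windows do not meet, so early-termination or unscheduled records from the following one to two weeks drop out of those by-visit tables

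*SAP*

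**What the plan says.** SAP Section 6.4 keeps scheduled visits at their nominal visit. For the rest it states that "data collected at early termination and unscheduled visits will be included and assigned to a visit window as described below". The rows that matter are those around Week 30:

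- **CDI-2 and C-SSRS.** The Week 30 window ends at "Week 30 visit date (or Day 224 if subject terminated before Week 30 visit"). The Week 34 window runs from Day 225 to Day 262.
- **Vital signs, weight and height.** The Week 30 window ends at "Week 30 visit date (or Day 217 if subject terminated before Week 30 visit"). The Week 32 window is "Day 218 - Day 231".
- **YGTSS.** The Week 30 limit is worded as for CDI-2, but the Week 34 window is "Day after Week 30 visit - 262".
- **ECG and laboratory tests.** The Week 28 window runs without a break from Day 127 to Day 287.

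Section 6.1 sets the consequence of being unmapped: "Only visits mapped to scheduled visits will be included in by-visit summaries". It also says that "All visit assessment data will be included in shift tables and will appear in the patient listings".

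**The concern.** In the two safety rows the end of the Week 30 window depends on whether the patient reached that visit, but the start of the next window does not. The pairs 224/225 and 217/218 meet only for patients who stopped before Week 30. For everyone who attended, the Week 30 window closes on the visit date, about Day 210, and nothing opens until Day 225 or Day 218. This conflicts with the statement in Section 6.4 that such data will be assigned to a window, and with the YGTSS row of the same section, which handles the same transition without a gap.

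At stake are the by-visit tables for Parts I and III combined. Safety is the primary objective, and CDI-2, C-SSRS and vital signs are named safety endpoints (Section 4.1). Table 3 schedules no CDI-2 or C-SSRS between Weeks 30 and 34, so early-termination and unscheduled assessments are the only such data from most of the blinded re-titration. CDI-2 is the most exposed: Section 9.11 plans summaries at each visit and no shift table.

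**Working it through.** The SAP gives no figure for this, so the check is to take each study day and ask whether it falls in a stated window.

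**Inputs.** The Week 30 visit is nominally Day 210 (Table 3). The tolerance comes from the footnote "Assessments to occur at end of study week (±3 days"), which gives Day 207 to Day 213. Blinded dosing is taken to start on Day 197 (Table 3 footnote); this does not affect the gap.

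**Formula.** Unmapped days = (first day of the next window − 1) − (last day of the Week 30 window).

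| Week 30 visit | CDI-2/C-SSRS | Vital signs, weight, height | YGTSS | ECG, laboratory |
|---|---|---|---|---|
| Day 207 | 224 − 207 = 17 (Days 208–224) | 217 − 207 = 10 (Days 208–217) | 0 | 0 |
| Day 210 | 224 − 210 = 14 (Days 211–224) | 217 − 210 = 7 (Days 211–217) | 0 | 0 |
| Day 213 | 224 − 213 = 11 (Days 214–224) | 217 − 213 = 4 (Days 214–217) | 0 | 0 |
| Terminated before Week 30 | 224 − 224 = 0 | 217 − 217 = 0 | 0 | 0 |

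For an on-schedule patient the CDI-2/C-SSRS gap covers 14 of the 21 days of blinded re-titration (Days 211 to 231).

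**What a repaired window would change.** Under the selection rules at the end of Section 6.4, a scheduled visit outranks an early-termination record, which outranks an unscheduled one. Three cases follow for a CDI-2 record on Day 218:

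1. The patient terminates then. Now the record is unmapped; with the windows joined it would represent Week 34. The table changes.
2. The record is unscheduled and the patient attends Week 34. Now it is unmapped; with the windows joined the scheduled visit is selected. The table does not change.
3. The record is unscheduled and the patient misses Week 34. Now it is unmapped; with the windows joined it is eligible for Week 34. The table can change.

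The same holds for vital signs on Days 211 to 217, with Week 32 in place of Week 34.

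**After the repair.** If both windows start on the day after the Week 30 visit, the unmapped days fall to 0 for all patients who attended it.

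**The case against.** The strongest reply is that little is lost. Scheduled visits are untouched, including vital signs at Week 32. Unscheduled CDI-2 and C-SSRS assessments are at the investigator's discretion (Table 3), and most would be outranked by a later scheduled visit anyway. Events in the gap are counted elsewhere: the C-SSRS shift table takes the worst category over Parts I and III (Section 9.13), the markedly abnormal vital-signs summary takes any qualifying value in those Parts (Section 9.7), adverse events, including the suicide/self-injury and depression SMQs, are allocated by date and not by visit window (Section 9.4), and the listings show everything. All of this stands and limits the size of the point. It does not rescue the CDI-2 value of a patient who terminates in the gap, which reaches only a listing.

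Three stronger readings are tempting but unsupported:

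- **That every by-visit safety table loses two weeks of data.** ECG and laboratory windows cover these days, and the vital-signs gap is about one week.
- **That the loss selects for patients doing badly.** The SAP gives no reasons for stopping in this interval.
- **That never-randomized patients are a major part of the problem.** Their Week 28 window ends on Day 203, so Days 204 to 224 are formally open for CDI-2/C-SSRS. But randomization takes place at Week 28, an early-termination visit is due as soon as possible after the last dose, and the SAP describes no route for such a patient to continue. The interval is therefore largely empty, and the YGTSS row has the same Day 203 limit.

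It is also fair to say that joining the windows labels some records with a distant visit. A Day 211 record would be shown as Week 34 (238 − 211 = 27 days early) or, for vital signs, as Week 32 (224 − 211 = 13 days early). The SAP already accepts this for YGTSS.

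**Conclusion.** The point holds in a limited form. For patients who attended Week 30, early-termination or unscheduled CDI-2/C-SSRS records on about Days 211 to 224 and vital signs, weight and height records on about Days 211 to 217 map to no visit and leave those by-visit summaries. The gap is 14 days (11 to 17) and 7 days (4 to 10) respectively, assuming that Week 30 takes place within ±3 days of Day 210.

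The tables change only for patients who terminate in the gap or miss the next scheduled visit. The SAP does not allow that number to be estimated; it is probably small. CDI-2 is affected most. The Part II comparison from Week 28 to Week 30 is not touched, because the gap begins after the Week 30 visit. This reads as a drafting slip: the fixed starts meet the limits meant for patients who stopped before Week 30 and were not adapted for the others.

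**What to change.** In Section 6.4:

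- Start the CDI-2/C-SSRS Week 34 window on the day after the Week 30 visit, or on Day 225 if the patient terminated before Week 30. Keep the end at Day 262.
- Start the vital signs, weight and height Week 32 window on the day after the Week 30 visit, or on Day 218 if the patient terminated before Week 30. Keep the end at Day 231.

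Two minor loose ends can be tidied in the same edit: the Week 30 window has no defined end for a patient who missed that visit but stayed in the study, and the Day 203 limit for patients not randomized leaves formally unassigned days.

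The cost is a few words in the SAP and a small change to the window derivation. No new data are needed and no scheduled record is displaced. The downside is the labelling noted above: some early-termination values will appear under a visit up to about four weeks later (CDI-2/C-SSRS) or about two weeks later (vital signs), which a table footnote can state.
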